### i. Co-Primary Outcome Measures

*Back-related dysfunction* will be measured with the Roland Disability Questionnaire ("Roland scale") which asks whether 24 specific activities were limited due to back pain during the past week (yes or no). This measure has been found to be reliable, valid and sensitive to clinical changes, and is appropriate for telephone administration and patients with moderate disability. This legacy questionnaire will be included as our primary outcome because we have used in all of our previous trials. We will also include the PROMIS physical function to see how they perform relative to each other.

*Pain* will be measured by asking participants how they would rate their back pain on average using a 1 to 10 numerical rating scale. This is likely to be very comparable to our previously used 0 to 10 scales to measure either the pain intensity or bothersomeness of back pain during the previous week on a 0 to 10 scale (0 = "not at all bothersome" and 10 = "extremely bothersome"). The validity of numerical rating scales of pain has been well documented, and such scales have demonstrated sensitivity to detecting change in pain after treatment.

### ii. Other Core Recommended Outcomes:

*Physical function* will be assessed using the 4-item PROMIS measure.

*Depression* will be assessed with the 4-item PROMIS measure, for which there is a published “crosswalk” to the Patient Health Questionnaire-8 (PHQ-9) which measures both depression severity and current DSM-IV depression diagnostic status and which we have used in prior studies.

Anxiety will be measured by means of the 2-item Generalized Anxiety Disorder scale (GAD-2), which has demonstrated high sensitivity and specificity in detecting generalized anxiety disorder in primary care populations [61, 62].

*Pain Interference* with normal daily activities will be measured with 4 PROMIS measure.

*Sleep disturbance* will be measured with the 4-item PROMIS measure.

*Patient Global Impression of Improvement* [of cLBP related dysfunction] will be asked on a seven point scale ranging from “very much improved” to “very much worse”. This standard rating has worked well in our prior studies.

### **iii. Selected Other Outcomes**

*Use of back-related medications and exercise* in past week will be measured on the 12, 26 and 52-week questionnaires to provide an indication of how these behaviors were affected by the interventions. They also provide an indication of “co-interventions” that occurred during the follow-up period.

*Qualitative outcomes:* Inclusion of open-ended questions in our previous trials has yielded valuable insights into participants’ feelings about the value of specific components of the interventions and the impact of the interventions on their lives. We will, therefore, include open-ended questions asking about these issues at the end of the 12, 26 and 52-week follow-up interviews.

*Fall outcomes:* The Short Physical Performance Battery is a group of physical performance tests that combines the results of gait speed, chair stand and balance test into one measures that predicts disability in diverse populations. The Four Square test is another reliable and valid measure of balance. Fear of falling will be measured with the well validated, 7-item short form version of the Falls Efficacy Scale – International.

### **iv. Maximizing Follow-up Rates and Documentation of Follow-up**

We will attempt to obtain outcome data from all RCT participants, including those who have moved out of state. We will collect information on the outcomes at every stage of our recruitment, randomization, and treatment process so that we can report patient flow according to the CONSORT guidelines, which is necessary for assessing the feasibility of the study. We will attempt to ensure high response rates by paying participants \$25 for each completed interview. We will calculate follow-up rates for our 12, 26 and 52-week interviews separately for the Tai Chi, Attention Control and Usual

Medical Care groups. In our other trials we have consistently achieved short-term follow-up rates over 90% and one-year follow-up rates of close to 90% in our previous RCTs evaluating CIM treatments for cLBP by keeping interviews reasonably short, and compensating participants for completing the interviews.

#### **v. Assessment of Feasibility:**

We will collect data on the key components of the feasibility trial from four sources: 1) feedback from members of the research team, 2) information from the Tai Chi instructor and consultant [name], 3) data collected during the feasibility trial (e.g., recruitment rates, class attendance, home practice, follow-up rates, adverse events), and 4) data from debriefing group discussions with 30 RCT participants (16 from Tai Chi, 6 from Attention Control and 8 from Usual Medical Care). At the 52-week follow-up, 30 participants (16 from Tai Chi, 6 from Attention Control and 8 from Usual Medical Care) will be invited to attend an intervention-specific group discussion (just after their final outcome assessment) to provide feedback on their experiences with all aspects of the study (e.g., recruitment process, Tai Chi or Attention Control protocols, outcome measures, adverse effects, home practice support procedures and materials).

### **7. ASSESSMENT OF SAFETY**

In a systematic review of adverse events in RCTs of Tai Chi, [name] and colleagues reported no serious adverse events. Other adverse events were primarily minor musculoskeletal pain (back and knee) and occasionally falls were reported.

#### **7.1 Methods and Timing for Assessing, Recording, and Analyzing Safety Parameters**

We will collect data on adverse events from several sources and incorporate them into a database. These sources are: 1) reports from the Tai Chi instructor(s) of any extraordinary occurrences of concern to them, 2) the questionnaires completed by participants at 12, 26 and 52-weeks will inquire about: any harm they felt from the Tai Chi classes or home practice, and any serious health problems, and 3) participants themselves because the consent form directs participants with injuries they believe may be related to the mind-body programs to call the Principal Investigator, Co-Investigators or the Human Subjects Representative, whose names and phone numbers are listed on the copy of the consent form retained by the participant.

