#### **SAFETY OUTCOMES**

Any adverse events identified during classes, on the follow-up interviews or through other means will be documented and reported on a regular basis to the Data Safety Monitoring Body (DSMB). Serious adverse events will be reported to the DSMB within 7 days. If attributable to the interventions, serious adverse events will also be reported to the IRB within 7 days.

---

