**TABLE 4. Schedule of Evaluations**

ASSESSMENT	Screening/ Baseline	Tai Chi Classes/ Attention Control	12/26- Wk	52- Wk
Informed Consent	x/			
Demographics [baseline]	/x			
Medical History [some screening, some baseline]	x/x			
Inclusion/exclusion criteria [screening]	x/		x	x
Physical Assessments	x		x	x
Questionnaire with Outcome Measures [see Table 3]	x		x	x
Enrollment/Randomization	/x			
Class Attendance		x		
Home Practice Logs		x		
Adherence to Tai Chi Protocol/Attention Control Protocol		x		
Adverse events		x	x	x
Qualitative discussion [subset of participants]		x	x	x

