We will modify our outcome measures in consultation with our patient partners in the Administrative Year prior to the RCT. Because older adults have a variety of symptoms, we might, for example, include the MYMOP measure, which allows patients to assess progress on their own desired outcomes from health care. Careful attention will be paid to ensure that the questionnaire is not too burdensome for older adults. We would aim for approximately 20 minutes for the follow-up questionnaires.

**TABLE 5:Content of Baseline and Follow-up Assessments  
SOURCES OF DATA FOR BACK TAI CHI TRIAL**

MEASURES	Baseline	12-Wk	26-Wk	52-Wk
BASELINE INFORMATION				
Patient characteristics (age, gender, ethnicity, race, employment status, education, height, weight, smoking status, excessive use of drugs or alcohol) (NIH Task Force Research Standards); education	x			
Back pain history (pain duration, leg pain, other pain sites, low back operation, use of selected treatments, work loss due to back pain, disability status, catastrophizing, fear avoidance)	x			
Expectations and knowledge of Tai Chi/Health Education	x			
CORE SET OF OUTCOMES FOR BACK PAIN STUDIES				
* Back dysfunction (24-item Roland Morris Disability Questionnaire-RMDQ)	x	x	x	x
* Low back pain intensity (0-10 numerical rating scale)	x	x	x	x
Pain interference (4-items PROMIS)	x	x	x	x
Pain Interference and enjoyment of life (2-items PEG)	x	x	x	x
Physical Function (4-items PROMIS)	x	x	x	x

Depression (4-items PROMIS)	x	x	x	x
Anxiety Screener (GAD-2)	x	x	x	x
Sleep disturbance (4-items PROMIS)	x	x	x	x
Patient Global Impression of Change (7 item scale)		x	x	x
Participant Disposition (see Section 6.4.iv)		x	x	x
TREATMENT-RELATED INFORMATION				
Adverse events		x	x	x
Perceptions of Tai Chi & HE classes, including instructors		x	x	
Adherence to assigned treatment, including home practice		x	x	x
Willingness to participate in a RCT of Tai Chi with an Attention Control (Cohort 1)	x			
POTENTIAL CONFOUNDERS				
Use of co-interventions (medications, other treatments, etc.)	x	x	x	x
Daily exercise and job-related activity	x	x	x	x
MEASURES FOR FALLS AND BALANCE				
Short Physical Performance Battery (balance, gait speed, chair stand)†	x	x	x	x
Four Step Square Test†	x	x	x	x
Fear of Falling	x	x	x	x

\*Co-Primary Outcome Measures

† Physical Assessment

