#### **7.2 Adverse Events and Serious Adverse Events**

We will define an **Adverse Event (AE)** as any unfavorable and unintended diagnosis, symptom, sign (including an abnormal laboratory finding), syndrome or disease which either occurs during the study, having been absent at baseline, or if present at baseline, appears to worsen. Adverse events will be recorded regardless of their relationship to the study intervention.

For this study, **Serious Adverse Events (SAE)** are defined as any research-related event (occurring at any dose or level of intervention) that results in any of the following outcomes:

- Death;

- Life-threatening event;
- Inpatient hospitalization or prolongation of existing hospitalization;
- A persistent or significant disability/incapacity; OR
- Any event that when based upon appropriate medical judgment may jeopardize the health or well-being of the subject and may require medical or surgical intervention to prevent one of the outcomes listed in this definition.

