### 7.3 Reporting Procedures

Adverse event data from the questionnaires will be provided to the Project Manager within a week (and will be transferred to the AE database). These will be reviewed, as will AE reports from all sources, by [name], with the assistance of Co-Investigator [name] (a psychologist) and [name] (a GHRI physician; Co-Investigator [name] will be available for geriatric specific issues)) on a weekly basis. Any SAEs identified will be reported promptly to the Kaiser Permanente Washington Human Subject Review Committee (the GH IRB) and the Independent Monitoring Committee (IMC). If an AE is reported by phone, the study staff member will complete an Adverse Events form, which will be entered into the database and will alert Project Manager [name] and PI [name] of the new AE report. If a SAE is identified by phone, it will be reported as outlined below. Adverse events that are not serious will be recorded and included in regular DSM Body reports, but will not be reported early to the IMC. Appendix A details adverse event reporting as required by the Kaiser Permanente Washington IRB.

Serious Adverse Events that are fatal will be reported to the IMC chair within 7 days of discovery, regardless of attribution. The table below details the adverse event reporting schedule and actions:

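### Section 7.1 describes no attribution-neutral question about non-serious adverse events in any arm, so it does not deliver the all-cause recording promised in 7.2

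*Protocol*

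**What the plan says.** Section 7.2 of the Protocol defines an adverse event broadly, as a new condition or the worsening of an existing one, and adds: "Adverse events will be recorded regardless of their relationship to the study intervention". The Precis (Safety Outcomes) is equally broad: "Any adverse events identified during classes, on the follow-up interviews or through other means will be documented".

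Table 4 (Schedule of Evaluations) marks adverse events in the column "Tai Chi Classes/ Attention Control" and at 12/26 and 52 weeks. Table 5 in section 6.4 lists them at 12, 26 and 52 weeks. A neighbouring row, "Perceptions of Tai Chi & HE classes, including instructors", names both class types, while the adverse event row carries no limit by arm.

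Section 7.1 names three sources:
- reports by the Tai Chi instructor of occurrences out of the ordinary;
- follow-up questionnaires on "any harm they felt from the Tai Chi classes or home practice, and any serious health problems";
- calls from participants with "injuries they believe may be related to the mind-body programs".

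The planned safety summary (Protocol 9.6 i, repeated in the SAP under Data Analyses) is the proportion of people reporting adverse events, with type and seriousness.

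For serious events, 7.2 confines the category to events related to the research. The Precis gives 7 days for reporting serious events to the monitoring body, the 7.3 text says promptly, and the reporting table in 7.3 sorts events by whether they are related to Tai Chi.

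**The concern.** The definition in 7.2 is all-cause, but the collection described in 7.1 is largely by attribution. A control participant cannot answer a question about harm from Tai Chi classes they did not attend. A Tai Chi participant with a new complaint that they do not connect with Tai Chi is not prompted to mention it unless it is serious.

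The Precis makes the rate and severity of adverse events one of the grounds for judging feasibility, and the monitoring committee works from the same data. If collection follows 7.1 as written, the reported proportion is a mixture: serious events of any cause in all arms, non-serious events attributed to Tai Chi in one arm, and whatever else happens to be volunteered. That is not the quantity 7.2 defines. If it were tabulated by arm, the arms would not have been asked the same thing.

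Falls illustrate the gap. Section 7 names them among events seen in Tai Chi trials, yet the fall outcomes in 6.4 iii are performance tests and a fear-of-falling scale. A minor fall not attributed to Tai Chi has no systematic question described for it. No passage promises a fall count, so this is an example and not a separate inconsistency.

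**Working it through.** The plan states no figure to reproduce. The check sets the passages side by side.

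**Step 1. Who is affected.** Arm sizes from the Protocol Precis and section 3: 39 Tai Chi, 15 Attention Control, 24 Usual Medical Care. Controls: 15 + 24 = 39, and 39/78 = 50%. (The SAP gives a total of 64 without arm sizes; the later Protocol's figures are used.)

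**Step 2. What each described route can reach.**

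| Route | Arms reached | Non-serious events of any cause? |
|---|---|---|
| Questionnaire item on Tai Chi harm (7.1) | Tai Chi | Only if attributed to Tai Chi |
| Questionnaire item on serious problems (7.1) | All | No, serious only |
| Instructor reports (7.1) | Tai Chi | Not a question to participants; unusual occurrences only |
| Participant calls (7.1) | Those who link an injury to the programs | No |
| Phone reports (7.3: "If an AE is reported by phone, the study staff member will complete an Adverse Events form") | Any | Yes, but unsolicited |
| Other means (Precis) | Any | Yes, but no question described |
| Observation of Tai Chi classes (5.1.6 iii) | Tai Chi | Difficulties seen in class |
| Qualitative discussion (Table 4; 6.4 v) | A subset of all arms | Possibly, for that subset |

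No row puts the same neutral question about non-serious events to every participant.

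**Step 3. Effect on the summary.** Write the all-cause proportion under 7.2 as P and the proportion recorded under 7.1 as R. Events that are not asked about and not volunteered are absent from R, so R can be at most P. The gap P − R depends on the true rate of non-serious events and on how many are volunteered. The documents give neither. The 15 to 29% in 9.6 i is mild transient pain during stretching or yoga in other studies. It is activity-related and cannot stand in for an all-cause rate.

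**Step 4. Serious-event reporting.** Take a non-fatal serious event at a health education class, or during a balance test at a follow-up visit. It is research-related, so it meets the 7.2 definition, and it is definitely not Tai Chi-related.
- Precis: to the monitoring body within 7 days.
- 7.3 text: promptly, to the IRB and the monitoring committee.
- 7.3 reporting table, row for non-fatal events not related to Tai Chi: with the regular reports.

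Promptly is compatible with 7 days. The table row is not on that clock: the row above it, for Tai Chi-related non-fatal events, states 7 days explicitly and this one does not. The table also has no category for events related to Attention Control or to study assessments. This step takes the differently named monitoring bodies to be the single committee of 7.5.

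**The case against.** **The questionnaire has not been seen.** Section 7.1 is a one-sentence summary, 7.3 refers to adverse event data from the questionnaires, Tables 4 and 5 schedule adverse events without an arm limit, and the Manual of Operations (10.3.1) is not in the documents. A neutral item may exist. This stands, and it limits the finding to what the plan describes.

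**Other measures pick up worsening in every arm.** Pain intensity, the Roland scale and global impression of change are asked of everyone at each follow-up, there are open-ended questions, and medical record data are collected for usual care. This stands in part. These measures bear mainly on back pain, 7.1 does not list them as adverse event sources, and no rule turns them into recorded events.

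**Attributed harm suits a feasibility study.** The summary is descriptive, its reference figure is activity-related, and no comparison by arm is planned. This is fair, and it is why the consequence is moderate. It does not reconcile 7.1 with 7.2.

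**The serious-event case is narrow.** Most unrelated events fall outside the 7.2 definition, and a report made within 7 days could also go into the regular reports. The case is indeed narrow. But someone following the table alone would have no reason to report within 7 days.

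**Conclusion.** The point holds for non-serious events. As 7.1 describes collection, 39 of 78 participants (50%) are not asked a systematic question about them, and the other 39 are asked only about those they attribute to Tai Chi. The proportion in 9.6 i would then not measure the all-cause rate in 7.2, and a tabulation by arm would not be comparable. This rests on the questionnaire matching its description in 7.1. Confidence is moderate.

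Stronger readings that the documents do not support:
- A reader might infer that controls are never asked about adverse events, or only at the 52-week debriefing. The question on serious problems reaches all arms, and the tables schedule adverse events and qualitative discussion at 12, 26 and 52 weeks without an arm limit. Counts of debriefing invitations do not measure ascertainment.
- A reader might infer a biased treatment comparison. None is planned for adverse events.
- A reader might infer that a serious event could wait six months. That assumes the regular reports are the six-monthly ones mentioned for protocol deviations in 10.3.2, which the table does not say.
- A reader might see a contradiction in the 3 days (table) and 7 days (7.3 text) for a Tai Chi-related death. One report can satisfy both, so this is a matter of alignment.

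The serious-event disagreement is real only for a non-fatal, research-related event that is definitely not Tai Chi-related.

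**What to change.** 1. At 12, 26 and 52 weeks, ask all three arms the same neutral question: any new or worsened health problem, including falls, since the last visit. Ask about attribution afterwards. If the questionnaire already does this, amend 7.1 to say so.
2. Have the Research Assistant who already attends the Attention Control classes (5.3) report events as the Tai Chi instructor does.
3. In 9.6 i and the SAP, take the adverse event proportion from the common question. Show attributed events separately, so that they can still be set against the 15 to 29% from the earlier studies.
4. Reconcile the serious-event definition, the relatedness categories (including Attention Control and study assessments) and the reporting times across the Precis, 7.2, the 7.3 text and the reporting table. No view is taken here on which is right.

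The cost is one or two questionnaire items and some redrafting, using staff already present. The downside is more non-serious events to log and review, and a higher reported adverse event rate.

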#### **7.2 Adverse Events and Serious Adverse Events**

We will define an **Adverse Event (AE)** as any unfavorable and unintended diagnosis, symptom, sign (including an abnormal laboratory finding), syndrome or disease which either occurs during the study, having been absent at baseline, or if present at baseline, appears to worsen. Adverse events will be recorded regardless of their relationship to the study intervention.

For this study, **Serious Adverse Events (SAE)** are defined as any research-related event (occurring at any dose or level of intervention) that results in any of the following outcomes:

- Death;

- Life-threatening event;
- Inpatient hospitalization or prolongation of existing hospitalization;
- A persistent or significant disability/incapacity; OR
- Any event that when based upon appropriate medical judgment may jeopardize the health or well-being of the subject and may require medical or surgical intervention to prevent one of the outcomes listed in this definition.

### 7.3 Reporting Procedures

Adverse event data from the questionnaires will be provided to the Project Manager within a week (and will be transferred to the AE database). These will be reviewed, as will AE reports from all sources, by [name], with the assistance of Co-Investigator [name] (a psychologist) and [name] (a GHRI physician; Co-Investigator [name] will be available for geriatric specific issues)) on a weekly basis. Any SAEs identified will be reported promptly to the Kaiser Permanente Washington Human Subject Review Committee (the GH IRB) and the Independent Monitoring Committee (IMC). If an AE is reported by phone, the study staff member will complete an Adverse Events form, which will be entered into the database and will alert Project Manager [name] and PI [name] of the new AE report. If a SAE is identified by phone, it will be reported as outlined below. Adverse events that are not serious will be recorded and included in regular DSM Body reports, but will not be reported early to the IMC. Appendix A details adverse event reporting as required by the Kaiser Permanente Washington IRB.

Serious Adverse Events that are fatal will be reported to the IMC chair within 7 days of discovery, regardless of attribution. The table below details the adverse event reporting schedule and actions:

**Table 4. Adverse Event Reporting Procedures**

Adverse Event	Action taking by study team
Serious	
Fatal	
Tai Chi Related a	Record on AE and SAE forms Report to DSM Body Chair within 3 days of discovery
Not Tai Chi Related b	Record on AE form Report to IMC within 7 days of discovery
Not Fatal	
Tai Chi Related a	Report on AE and SAE forms Report to IMC within 7 days of discovery
Not Tai Chi Related b	Record on AE form Report to IMC as part of regular reports
Not Serious	Record on AE form

a possibly, probably or definitely

b definitely not

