## **6.4 Follow-up Visits**

To maximize response rates, reminder letters will be sent before each follow-up visit. The contents of the in-person follow-up visits (12, 26 and 52 week) is shown in Table 2. While participants are provided an opportunity to complete their assessments in a group format (with instructions not to discuss their group assignment), physical assessments (Short Physical Performance Battery, Four Square Step Test, Gait Speed) will take place in a private room adjacent to the group area. The follow-up questionnaire will be administered using either a study tablet computer or a paper questionnaire, whichever the participant prefers. Questions about experiences with specific aspects of the Tai Chi intervention that might cause participants to think differently about their outcomes will be asked at the end of an interview, after all other outcomes are

assessed. We will attempt to obtain outcome data from all participants in the trial. The Research Specialist, masked to study group, will be present and available to answer any questions that might arise while the participant is completing the follow-up questionnaire. Our patient partners will be asked about the value of the group format at follow-up and the likelihood we can maintain our masking with multiple participants in a room. If this is believed unfeasible, we will schedule visits in the same location (GH clinic classroom) for one individual at a time.

The NIH Task Force on Research Standards for Chronic Low Back Pain made recommendations for a core set of baseline outcomes. These measures include many of the key outcome domains recommended for us used in trials of chronic low back pain. We will therefore include all of these in our questionnaire along with a few others. Table 3 summarizes the measures, with the NIH Task Force recommendations being shaded in blue. Relevant additional secondary measures of interest for virtually all older adults include scales assessing fear of falling and measures of balance.

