### **10.3.2 Protocol Deviations**

Protocol deviations will be captured through weekly review of study recruitment and follow-up reports and through routine bi-weekly data checks of study data being collected, entered, and stored in our study databases. The weekly review of study recruitment and follow-up reports will be conducted by PI, [name] and Project Manager [name]. The bi-weekly data check of the study databases will be performed by the programmer and reviewed by PI [name] and Project Manager [name]. In addition, study staff responsible for conducting these activities will meet with Project Manager [name] on a weekly basis to discuss study progress and any potential violations that may have occurred. Protocol violations will be reported to the Kaiser Permanente Washington IRB as a part of the annual continuing review report. In addition, protocol violations will be reported to the Independent Monitoring Committee as a part of the reports completed every six months during active recruitment, intervention, and follow-up periods.

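### The reporting table speeds a non-fatal SAE to the monitoring committee only if it may be due to Tai Chi, so serious harm caused by another part of the study can wait for a regular report, contrary to the precis and the 7.3 text

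*Protocol*

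**What the plan says.** Four parts of the Protocol bear on how fast a non-fatal SAE reaches the monitoring body.

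- **Precis, Safety Outcomes:** "Serious adverse events will be reported to the DSMB within 7 days". No condition on cause is attached. The sentence after it restricts only IRB reporting, to events attributable to the interventions.
- **Section 7.3, text:** "Any SAEs identified will be reported promptly to the Kaiser Permanente Washington Human Subject Review Committee (the GH IRB) and the Independent Monitoring Committee". The same section holds back early notice to the IMC only for events that are not serious.
- **Section 7.3, Table 4 (Adverse Event Reporting Procedures):** a non-fatal SAE that is possibly, probably or definitely Tai Chi related has the action "Report to IMC within 7 days of discovery", on AE and SAE forms. One that is definitely not Tai Chi related goes on an AE form only, with the action "Report to IMC as part of regular reports". Fatal events go within 3 days if Tai Chi related and within 7 days if not.
- **Section 7.2:** SAEs "are defined as any research-related event (occurring at any dose or level of intervention") with a serious outcome. The scope is the research, not Tai Chi alone.

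Table 4 does not say how often regular reports are made. The only interval given for IMC reports is in section 10.3.2, which places protocol violations in "reports completed every six months during active recruitment, intervention, and follow-up periods".

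**The concern.** The table sorts events by relation to Tai Chi, while the SAE definition sorts by relation to the research. Between the two lies serious harm that the study caused but Tai Chi did not. The trial has two obvious sources of it. One is the Attention Control classes. The other is the "physical assessments (Short Physical Performance Battery, Four Square Step Test, Gait Speed") done in every arm at 12, 26 and 52 weeks, in people aged 65 or over. If a Usual Medical Care participant falls and is hospitalised during the stepping test, the event is plainly caused by the study and definitely not caused by Tai Chi. Table 4 puts it on the slow route.

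Under 7.5 the IMC may recommend changing or ending the trial, but it can act only on events it has been told about. What is at stake is timely independent review of study-caused serious harm, possibly before the next round of the same tests.

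**Working it through.** The plan states no figure for this, so the first step compares the texts. The rest sizes the delay and the exposure.

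**1. Same event, three instructions.** Take a non-fatal SAE that is research-related and definitely not Tai Chi related.

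| Source | Time to the monitoring body |
|---|---|
| Precis | 7 days |
| 7.3 text | promptly |
| 7.3, Table 4 | next regular report |

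Promptly might be read as whatever the table lays down. Seven days cannot be. The comparison treats DSMB and IMC as one body; 7.5 describes only the IMC.

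If SAE is read more widely than 7.2 allows, so that an unrelated hospital stay counts, the precis and the table still disagree about it. If 7.2 is applied strictly, such a stay is not an SAE and no conflict arises for it.

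**2. Delay.** Six months is taken as 26 weeks (inferred from 10.3.2), with events falling at random in the cycle.

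- Longest wait: 26 × 7 = 182 days, against 7 days.
- Mean wait: 182 / 2 = 91 days.

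**3. What the delay means in practice.**

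- *Injury at the 12-week assessments.* The next round is 26 − 12 = 14 weeks later. The chance that it starts before the IMC hears is (26 − 14) / 26 = 12/26 = 46%. Under a 7-day rule it is 0%.
- *Event in an Attention Control class.* The series lasts 12 weeks. For an event at a random point, the mean time left is 6 weeks, so the chance that the IMC hears before the series ends is 6/26 = 23%. If every report took the full 7 days, it would be 11/12 = 92%.

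**4. How often it could arise.** The relevant participants are those for whom a Tai Chi cause can be ruled out: 15 Attention Control + 24 Usual Medical Care = 39.

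- Follow-up assessments, all attended: 39 × 3 = 117.
- Attention Control person-classes, all attended: 15 × 24 = 360.

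The documents give no rate of serious injury per assessment. Assume p between 1 in 10,000 and 1 in 1,000. The chance of at least one in 117 is 1 − (1 − p)^117:

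- p = 0.0001: 1 − 0.9999^117 = 1.2%
- p = 0.001: 1 − 0.999^117 = 11%

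Expected events are 117 × 0.0001 = 0.01 to 117 × 0.001 = 0.12. No rate is assigned to the classes, which are health-education talks with discussion.

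**The case against.** The strongest reply is that the governing schedule can be identified. Section 7.3 says "The table below details the adverse event reporting schedule and actions", and a precis is only a summary. The slow row is also narrow: the footnotes send every possibly related event to the 7-day row, so only events graded definitely not Tai Chi related remain. That row was probably written for unrelated hospital stays, for which a regular report is reasonable. Deaths go within 7 days whatever the cause. The IRB has its own route in 7.3 and Appendix A, and the study team reviews adverse event reports weekly.

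All of this limits the point without removing it. If the table governs, it is the table that sends study-caused harm to a regular report. The footnote does not help a control participant, whose injury on a balance test is correctly graded definitely not Tai Chi related.

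Three stronger readings are tempting, and the documents support none of them.

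- *Staff cannot comply with both rules.* They can: notice within 7 days, repeated in the regular report, satisfies every text. Table 4 does not forbid early notice; it merely fails to ask for it.
- *All follow-up assessments are exposed.* That would be 78 × 3 = 234, but half belong to Tai Chi participants, whose fall on a test may well be graded possibly Tai Chi related and expedited. The control-arm count of 117 is the defensible one.
- *Section 9.4 repeats the same limit in its stopping condition.* It does not. Section 9.4 refers to SAEs in the Tai Chi arm, whatever their cause, whereas Table 4 limits by attribution. Sections 7.5 and 11.5 already give broader grounds for stopping, so the 9.4 wording is at most an editorial matter.

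**Conclusion.** The point holds as an inconsistency in the safety reporting rules with a small but real consequence. Followed as written, Table 4 can delay the IMC's knowledge of study-caused, non-fatal serious harm to about 182 days (mean 91), where the precis gives 7. At the assumed per-assessment risks, the chance that this arises at least once in the control-arm follow-up tests is 1.2% to 11%. Events in the 360 Attention Control person-classes would add to that by an unknown, probably small, amount.

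This rests on three assumptions: that regular reports are the six-monthly ones of 10.3.2, that DSMB and IMC name one body, and that the event rates lie in the range shown. The conflict in the text needs only the second. A reader might infer that such harm would escape oversight altogether. The documents do not support that, since IRB reporting and weekly team review continue. What is lost is timely independent review. The change is worth making because it is cheap, not because the risk is large.

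**What to change.** 1. **Table 4 in section 7.3:** relabel the related rows *at least possibly related to the study*, a term that Appendix A already uses, and the other rows *definitely not related to the study*. Keep the time limits.
2. **Section 7.2:** delete the research-related condition from the SAE definition. The table already grades relatedness, and its unrelated rows make no sense under the present definition.
3. **Precis and the 7.3 sentence on SAEs:** state the same schedule as the table, saying openly that definitely unrelated non-fatal SAEs go in regular reports. Give the interval of those reports, and use one name for the monitoring body.

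The costs are small and should be stated. The SAE category widens to include unrelated serious events. A rare study-related SAE not due to Tai Chi needs a 7-day report. A death related to the study but not to Tai Chi moves from a 7-day to a 3-day report. For definitely unrelated non-fatal events, the precis gives up its faster rule. Visits and participant procedures are unchanged.

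As an editorial note only, 9.4 could be worded in terms of participant safety in any arm in the same amendment.
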